3.8.3 Local Site Reaction

Local site reactions include any reaction that occurs within the treatment area of subjects. Local site reactions are prespecified in the protocol and will be collected independently of

adverse events. Local site reactions that require medical intervention or extend beyond the treatment area will be documented as adverse events. At Visits 2 (Post-Treatment Assessment) and 3 (Test of Cure), subjects will be assessed at treatment area for the following 7 symptoms:

- Erythema
- Petechiae
- Erosion/ulceration
- Edema
- Burning/stinging
- Pain
- Pruritus (itching)

Subjects need to rate them as

- 1 = Absent,
- 2 = Mild (slight, barely perceptible),
- 3 = Moderate (distinct presence), or
- 4 = Severe (marked, intense).

These data, along with the following 2 questions on the same CRF, will be summarized categorically by visit.

- Did the local site reaction extend beyond the treatment area and was recorded as an AE? ("Yes", "No")
- Did the local site reaction require medical intervention? ("Yes", "No")

3.8.4 Vital Signs and Weight

Vital signs measurements, done at all study visits, include heart rate, pulse rate, respiratory rate, body temperature, systolic and diastolic blood pressures, in addition to height and weight. BMI (unit: kg/m²) will be calculated from height (inch) and weight (lb):

$$\text{BMI} = \text{Weight (lb)} / (\text{Height (inches)})^2 \times 703$$

Then it will be categorized as: Underweight (< 18.5), Normal (18.5 – 24.9), Overweight (25.0 – 29.9), and Obese (≥ 30.0). Both numerical and categorical summaries for BMI will be presented. The 6-number summary statistics for continuous variables and their changes from baseline, as well as the number and percentage of subjects in each BMI category will be presented by study visit and treatment arm.

3.8.5 Physical Examination

Physical examination will be performed at all study visits in the following body areas:

- Dermatological
- Respiratory
- H.E.E.N.T
- Cardiovascular
- Gastrointestinal
- Hepatic/Biliary
- Genitourinary/Reproductive

- Renal
- Neurological/Psychological
- Musculoskeletal
- Metabolic
- Hematological
- Immunological/Allergies
- Recent Trauma (past 3 months)
- Prior Surgery
- Congenital
- Other

The examination results (“Normal”, “Abnormal”), and changes from baseline (“Improved” – if “Abnormal” at baseline and “Normal” at post-baseline, “No Change”, “Worsened” – if “Normal” at baseline and “Abnormal” at post-baseline), will be summarized by presenting the number and percentage of subjects in each category by body area and treatment at each study visit.

3.8.6 Gynecological Exam

Gynecological exam will be done at each study visit in the following areas:

- Breasts
- Adnexae
- Vulva
- Vaginal wall
- Cervix
- Uterus
- Rectal

The examination results (“Normal”, “Abnormal”), and changes from baseline (“Improved” – if “Abnormal” at baseline and “Normal” at post-baseline, “No Change”, “Worsened” – if “Normal” at baseline and “Abnormal” at post-baseline), will be summarized categorically by visit.

For “Abnormal” results, a further question “Was the result clinically significant?” will also be summarized with number of “Yes” subjects.

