3.3.1 Inclusion Criteria

Subjects meeting all of the following criteria at Entry Visit (Visit 1) may be considered for study participation:

1. Non-pregnant female aged ≥ 18 years who is in good general health
2. Diagnosis of BV, defined as presence of all of the following:
 - a. Clinical diagnosis of BV (e.g., off-white [milky or gray], thin homogeneous discharge with minimal or absent pruritus and inflammation of the vulva and vagina); AND
 - b. Saline wet mount of vaginal discharge demonstrating the proportion of clue cells to be $\geq 20\%$ of the total epithelial cells; AND
 - c. Vaginal secretion pH > 4.5 , using pH paper that measures from 4.0 to 6.0; AND
 - d. Positive (fish odor) “whiff test” after addition of a drop of 10% potassium hydroxide (KOH) to vaginal discharge.
3. Willing to refrain from vaginal sexual intercourse on Days 1 to 7 (i.e., during treatment and for two post-treatment days) and for 48 hours prior to Visits 2 and 3.
4. Willing to refrain from using any intravaginal product (e.g., spermicide, tampon, douche, feminine deodorant spray, diaphragm, vaginal ring birth control, or condom with spermicide or insertion into the vagina of any drug or non-drug product during treatment), other than study treatment for the duration of the trial.
5. Subjects of childbearing potential who have a negative urine pregnancy test at the Entry Visit (Visit 1) and agree to use an acceptable form of birth control throughout the study. Acceptable forms of birth control include oral contraceptives (the pill), intrauterine devices (IUDs), contraceptive implants under the skin, patches or injections, and condoms without spermicide. Oral or transdermal hormonal contraceptives must be in use for one full cycle (e.g., four to eight weeks) prior to test article application. Injectable or implanted contraceptives (e.g., Depo-Provera, Nexplanon, or hormonal IUD) must be injected/inserted at least seven days prior to test article application. Subjects who are not of childbearing potential, as defined below, must also have a negative urine pregnancy test prior to randomization:
 - a. Postmenopausal for at least one year prior to the Entry Visit (Visit 1) (defined as ≥ 50 years of age and amenorrheic for $>$ one continuous year) or
 - b. Surgically sterile (defined as bilateral tubal ligation, bilateral oophorectomy, or hysterectomy) at least 6 months before first dose or

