3.1.2 Analysis Conventions

This section details general approaches to be used for the statistical analyses. Departures from these general approaches may be outlined in the specific detailed sections of this statistical analysis plan, and will take precedence over the general approaches. The following approaches will be applied to all data presentations and analyses.

- Data listings will be provided for all CRF data with one listing for one CRF panel. All data listings will be sorted for presentation in the order of site identifier (ID), subject ID, and date of procedure or event.
- Statistical summary tables will be provided for most CRF data, and generated for each of the 3 treatment groups, and for overall subjects (i.e., 3 groups combined) when appropriate.
- Summary statistics will consist of the number and percentage of responses in each category for discrete (categorical) variables, and the number of non-missing observations (n), mean, median, standard deviation (SD), minimum, and maximum (abbreviated as “6-number statistics”) for continuous variables.
- All mean values will be formatted to one more decimal places than the measured value, and standard deviation values will be formatted to two more decimal places than the measured value. For median values, the same decimal place as the measured values will be reported, if that is feasible without losing accuracy; otherwise, median values will be formatted to one more decimal place than the measured values.
- All percentages will be rounded to one decimal place. The number and percentage of categorical responses will be presented in the form XX (XX.X), where the percentage is in the parentheses. The denominator for percentage calculations will be the number of non-missing observations (n) when this number is shown, or will be the total sample size of the relevant treatment group for tables like adverse events, medical histories, or other tables where this number of non-missing observations (n) is not presented.
- All statistical tests will use a significance level of $\alpha = 0.05$. Two-tailed tests will be performed for all analyses that use statistical testing.
- All p-values will be rounded to 3 decimal places. All p-values that round to 0.000 will be presented as ‘<0.001’, and p-values that round to 1.000 will be presented as ‘>0.999’. Any p-value ≤ 0.05 will be considered statistically significant and will be marked with one asterisk (e.g., 0.025*).

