- All analysis and summary tables will have the population sample size in the column heading.
- Baseline is defined as the last data point on or before the day of randomization.
- Calculating change from baseline to a visit will be done as follows: Change from Baseline = Observed value at the visit – Baseline value.
- Subjects who have only baseline (without any post-baseline measurements) for a parameter at a visit, or only have post-baseline value for a parameter at a visit, will be excluded from the summary of change from baseline by visit for that parameter.
- Version 9.4 of SAS® or higher will be the statistical software package used to produce all statistical analysis tables and data listings.

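### The gynecological-exam change score in SAP 3.8.6 labels a move from not clinically significant to clinically significant as unchanged, and leaves the denominator for worsening unstated

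*SAP*

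**What the plan says.** SAP 3.8.6 covers seven exam areas, among them vulva, vaginal wall and cervix, each recorded as Normal or Abnormal at every visit. Change from baseline has three labels:

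- *Improved* and *No Change* appear as "Improved” – if “Abnormal” at baseline and “Normal” at post-baseline, “No Change". No definition of *No Change* follows.
- *Worsened* is the reverse transition only: "if “Normal” at baseline and “Abnormal” at post-baseline), will be summarized categorically by visit".

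The section adds a significance item: "For “Abnormal” results, a further question “Was the result clinically significant?” will also be summarized with number of “Yes” subjects". It does not link this answer to baseline or use it in the change label.

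Section 3.8.6 gives no denominator. The general rule in SAP 3.1.2 is "The denominator for percentage calculations will be the number of non-missing observations (n) when this number is shown"; otherwise it is the treatment-group size. The same section removes only women who lack a baseline or a post-baseline value: they "will be excluded from the summary of change from baseline by visit for that parameter". Women Abnormal at baseline are not removed.

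SAP 3.8.5 applies the same two-level rule to the physical examination, which has a genitourinary/reproductive row, and says that results "will be summarized by presenting the number and percentage of subjects in each category by body area and treatment at each study visit".

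**The concern.** A two-level score cannot register change within Abnormal. If a woman has a minor finding at Visit 1 that the investigator calls clinically significant at Visit 2, the table reports no change, although both answers are on the case report form. This is deterioration that a safety table should show by arm.

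The second issue is the denominator. A woman already Abnormal is not at risk of being *Worsened* under this rule. If she stays in the denominator, the printed percentage is smaller than the rate among women who could worsen, and nothing in 3.8.6 tells the reader so.

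The table serves the secondary objective, safety and tolerability against reference and vehicle. What is at stake is the accuracy of one descriptive summary of the treated area.

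**Working it through.** **Which transitions are mislabelled.** Splitting Abnormal by the significance answer gives three levels: N (Normal), A− (Abnormal, not clinically significant) and A+ (Abnormal, clinically significant).

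| Baseline → visit | Label under SAP 3.8.6 | Three-level reading |
|---|---|---|
| N → N | No Change | same level |
| N → A− | Worsened | higher |
| N → A+ | Worsened | higher |
| A− → N | Improved | lower |
| A− → A− | No Change | same level |
| A− → A+ | No Change | **higher** |
| A+ → N | Improved | lower |
| A+ → A− | No Change | **lower** |
| A+ → A+ | No Change | same level |

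Two of the nine cells are mislabelled; the one that matters for safety is A− → A+. The planned count of clinically significant results does not recover it. At a post-baseline visit that count is the sum of N → A+, A− → A+ and A+ → A+, and marginal totals by visit do not separate the three.

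**Denominator.** The plan states no figure to reproduce, so this is algebra with assumed inputs. Let q be the share Abnormal at baseline in an area and w the probability of Normal-to-Abnormal among women Normal at baseline.

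- Printed *Worsened* share, all examined women as denominator: (1−q) × w.
- Share among women Normal at baseline: w.
- Ratio of the two: 1−q.

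The documents give neither q nor w. Taking w = 10% and the planned 246 women per arm (Protocol 3.1; the number with both exams can only be smaller):

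| q (assumed) | Printed *Worsened* | Among Normal at baseline | 246 × q × w |
|---|---|---|---|
| 5% | 9.5% | 10% | 1.2 |
| 10% | 9.0% | 10% | 2.5 |
| 20% | 8.0% | 10% | 4.9 |
| 30% | 7.0% | 10% | 7.4 |
| 50% | 5.0% | 10% | 12.3 |

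Example at q = 20%: 246 × 0.80 = 196.8 women Normal at baseline; 196.8 × 0.10 = 19.7 *Worsened*; 19.7/246 = 8.0%, against 19.7/196.8 = 10%. The last column is the number of women per arm who would deteriorate within Abnormal and be labelled *No Change*, if w also applied to them. That is a further assumption.

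**Between-arm comparison.** With q equal across arms, (1−q) cancels from the ratio and multiplies the difference. An assumed 10% v 3% among women Normal at baseline prints as 8% v 2.4% at q = 20% and 5% v 1.5% at q = 50%. The ratio is 3.33 each time; the difference goes from 7 points to 5.6 and 3.5.

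**What the planned output already allows.** SAP 3.8.6 summarizes the results as well as the change labels. For women with both exams:

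- Abnormal at both = post-baseline Abnormal − *Worsened*.
- Normal at baseline = (post-baseline Normal − *Improved*) + *Worsened*.

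So the at-risk denominator can largely be rebuilt by subtraction. The A− → A+ cell cannot.

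**The case against.** The strongest answer is that the safety plan does not rest on this table, and that is right.

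- Erythema, petechiae, erosion/ulceration and edema are graded on four levels at Visits 2 and 3 (Protocol 4.7.1, SAP 3.8.3, Table 14.3.5).
- Deterioration of a condition present at baseline is an adverse event (Protocol 8.1.1.1), and SAP 3.8.2 defines treatment-emergent events to include it.
- Clinically significant abnormal results are counted, and Listing 16.2.9.3 gives each subject's exam.

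A reader might infer that new vaginal damage on top of a baseline abnormality would be invisible, or that this is the only before/after comparison of the treated organ. The documents support neither: the routes above exist, and SAP 3.8.5 has a genitourinary/reproductive row, though under the same two-level rule. These routes have limits. Local site reactions have no Visit 1 value. They must be recorded as adverse events only if they need medical intervention or extend beyond the treatment area. The significance count is not a shift from baseline.

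Other points that stand:

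- The denominator is inferred from 3.1.2, which lets specific sections depart from it, and the table shells are a separate document not available here.
- Entry criterion 2a describes "thin homogeneous discharge with minimal or absent pruritus and inflammation of the vulva and vagina", which argues for a low q for tissue findings.
- A reader might also expect the active arms to look safer because cured women move to *Improved*. That requires BV discharge to make an exam area Abnormal. The documents do not say so, and SAP 3.7.1 takes discharge from a different case report form page.

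What the objection does not answer is the label itself: no planned summary table shows, against baseline and by arm, a move from not significant to clinically significant.

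**Conclusion.** A minor but real defect in one descriptive table. By elimination, SAP 3.8.6 labels A− → A+ as *No Change*. That follows from the text, given that no other category can hold Abnormal-to-Abnormal.

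The dilution of the *Worsened* percentage by (1−q) is conditional on the 3.1.2 denominator applying. Its size is unknown because q is not given: negligible at 5%, a halving at 50%, and probably towards the low end for tissue findings. It leaves the between-arm ratio unchanged when q is balanced, as randomization gives in expectation, and it can largely be undone by subtraction. No test, threshold or decision depends on the table.

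The label's 9% rate of vulva/vaginal irritative symptoms should not be used to turn this into a number of missed women. It is a symptom rate under once- or twice-daily dosing, not a rate of new exam abnormality.

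**What to change.** In SAP 3.8.6 and Table 14.3.8, replace the two-level change score with a baseline-by-visit shift table, by exam area and arm, on three levels: Normal; Abnormal, not clinically significant; Abnormal, clinically significant. Define *Worsened* as any move to a higher level. Also report the Normal-to-Abnormal percentage with women Normal at baseline as the stated denominator.

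This needs SAP wording and one reprogrammed table. It needs no new data, assuming the significance question is answered at Visit 1 as at later visits; 3.8.6 attaches it to abnormal results without limiting the visit.

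The downsides are a larger table and a remaining blind spot: a new finding that leaves the significance level unchanged, at either Abnormal level, still shows as no shift. For those women the local site reaction table, the adverse events and the listing remain the sources.

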3.8.7 Other Safety Assessments

Other study assessments, such as pregnancy test (and pregnancy outcome, if known), and urine drug screen will be provided in data listings.

5.0 APPENDICES

5.1 Study Schedule of Assessments

Visit	Visit 1	Visit 2	Visit 3	Early Termination ^a
Visit Name	Entry Visit	Post-Treatment Assessment	Test of Cure	
Study Day(s)	1	8 to 15 days	22 to 31 days	
Informed consent	X			
Inclusion/exclusion criteria	X			
Demographics	X			
Medical and gynecological history	X			
Physical examination	X		X	X
Pelvic examination	X	X	X	X
Height	X			
Weight	X		X	X
Vital signs (after sitting for 5 - 10 mins)	X	X	X	X
Concomitant medications	X	X	X	X
Randomization ^b	X			
Dispense study medication ^c and dosing instructions	X			
Collect study medication		X		X ^d
Assessment of local site reactions		X	X	X
Adverse events	X	X	X	X
Urine pregnancy test	X	X	X	X
Urine drug screen	X			
Amsel's criteria evaluations:				
-Assessment of vaginal discharge	X	X	X	X
-KOH Whiff Test	X	X	X	X
-Saline Wet Mount	X	X	X	X
-pH	X	X	X	X
Collection of samples for Nugent's score based on Gram stain (send to central laboratory)	X		X	X
Collection of samples for STI assessment ^e (send to central laboratory)	X			

- a. At any time a subject decides to discontinue her participation in the study or is discontinued from the study for any other reason, she will be advised to complete the Early Termination procedures.
- b. Randomization to occur if the results of the full set of Amsel's criteria are positive.
- c. Study medication will be dispensed at Visit 1. The subject will be instructed to self-administer study medication intravaginally once daily at bedtime for 5 consecutive days.
- d. Unless collected at previous visit.

e. Central laboratory analysis for *Chlamydia trachomatis* and *Neisseria gonorrhoeae*.

5.2 Table of Contents for Data Display

Following is the list of planned tables and listings. Tables will be numbered according to the nomenclature used to support the final CSR. The datasets in the OGD Guidance will be created and used in our programming of the tables in this SAP.

The format of each unique table is provided in a separate document of “Table Shells”, but no data listing shells are provided. Final outputs may be slightly different in layout from that of illustrated in “Table Shells”. The table shells will not be amended to match the actual tables in such cases.

Table Number	Table Title	Analysis Population
14.1.1	Summary of Subject Disposition and Reasons for Discontinuation	All Screened
14.1.1.1	Screen Failure Reason Summary	Screen Failure
14.1.2	List of Subjects Who Prematurely Discontinued the Study	ITT
14.1.3	Summary of Subject Disposition by Study Site	ITT
14.1.4	Number and Percentage of Subjects at Each Visit	ITT
14.1.5	Summary of Protocol Deviations	ITT
14.1.6	Summary of Analysis Populations	ITT
14.1.7	Demographics	ITT
14.1.7S	Demographics	Safety
14.1.7M	Demographics	mITT
14.1.7P	Demographics	PP
14.1.8.1	Medical History	ITT
14.1.8.2	Gynecological History	ITT
14.1.8.3	Pregnancy History	ITT
14.1.8.4	Substance Use	ITT
14.1.9.1C	Number and Percentage of Subjects with Prior Medication Use by Drug Class in Descending Order of Frequencies	ITT
14.1.9.1G	Number and Percentage of Subjects with Prior Medication Use by Drug Generic Name in Descending Order of Frequencies	ITT
14.1.9.1	Number and Percentage of Subjects with Prior Medication Use by Drug Class and Generic Name	ITT
14.1.9.2C	Number and Percentage of Subjects with Concomitant Medication Use by Drug Class in Descending Order of Frequencies	Safety

14.1.9.2G	Number and Percentage of Subjects with Concomitant Medication Use by Drug Generic Name in Descending Order of Frequencies	Safety
14.1.9.2	Number and Percentage of Subjects with Concomitant Medication Use by Drug Class and Generic Name	Safety
14.1.9.3C	Number and Percentage of Subjects with Prior Medications Also Used After the Randomization by Drug Class in Descending Order of Frequencies	Safety
14.1.9.3G	Number and Percentage of Subjects with Prior Medications Also Used After the Randomization by Drug Name in Descending Order of Frequencies	Safety
14.1.9.3	Number and Percentage of Subjects with Prior Medications Also Used After the Randomization by Drug Class and Generic Name	Safety
14.2.1	Analysis of Therapeutic Equivalence	PP
14.2.2	Analysis of Study Sensitivity	miITT
14.2.3M	Summary of Bacteriological Cure and Therapeutic Cure	miITT
14.2.3P	Summary of Bacteriological Cure and Therapeutic Cure	PP
14.2.4M	Nugent's Score and Amsel's Criteria Summary by Study Visit	miITT
14.2.4P	Nugent's Score and Amsel's Criteria Summary by Study Visit	PP
14.3.0	Treatment Exposure and Compliance	Safety
14.3.1.1	Overall Number and Percentage of Subjects with Adverse Events	Safety
14.3.1.2	Overall Number of Adverse Events by Severity and Relatedness to the Study Treatment	Safety
14.3.1.3C	Summary of Adverse Events by System Organ Class in Descending Order of Frequencies	Safety
14.3.1.3P	Summary of Adverse Events by Preferred Term in Descending Order of Frequencies	Safety
14.3.1.4	Summary of Adverse Events by System Organ Class and Preferred Term	Safety
14.3.1.5C	Summary of Adverse Events by System Organ Class and by Severity	Safety
14.3.1.5	Summary of Adverse Events by System Organ Class and Preferred Term and by Severity	Safety
14.3.1.6C	Summary of Adverse Events by System Organ Class and by Relatedness to the Study Treatment	Safety

14.3.1.6	Summary of Adverse Events by System Organ Class and Preferred Term and by Relatedness to the Study Treatment	Safety
14.3.2.1	List of Serious Adverse Events	Safety
14.3.2.2	List of Adverse Events that Led to Premature Study Discontinuation	Safety
14.3.5	Local Site Reaction	Safety
14.3.6	Vital Signs and Weight	Safety
14.3.7	Physical Examination	Safety
14.3.8	Gynecological Examination	Safety

Listing Number	Listing Title	Analysis Population
16.2.1.1	Subject Information	All Screened
16.2.1.2	Inclusion / Exclusion Criteria Not Met	All Screened
16.2.1.3	Subject Disposition	ITT
16.2.1.4	Subject Study Visits	ITT
16.2.2	Protocol Deviations	ITT
16.2.3	Subjects Excluded from the Efficacy Analysis	ITT
16.2.4.1	Demographics	ITT
16.2.4.2	Medical History	ITT
16.2.4.3	Gynecological History	ITT
16.2.4.4	Pregnancy History	ITT
16.2.4.5	Prior and Concomitant Medications	ITT
16.2.4.6	Substance Use	ITT
16.2.5.1	Drug Accountability	ITT
16.2.5.2	Treatment Exposure	ITT
16.2.6.1	Study Procedures	ITT
16.2.7.1A	Adverse Events – Part A	ITT
16.2.7.1B	Adverse Events – Part B	ITT
16.2.7.2	Local Site Reaction	ITT
16.2.8.1	Nugent's Scores	ITT
16.2.8.2	Sexual Transmitted Infection Tests	ITT
16.2.9.1	Vital Signs	ITT
16.2.9.2	Physical Examination	ITT
16.2.9.3	Gynecological Examination	ITT
16.2.9.4	Pregnancy Test	ITT

16.2.9.5	Pregnancy Notification	ITT
16.2.9.6	Pregnancy Outcome	ITT
